Cohort 1 will enroll from 3 to 6 DLT-evaluable subjects administering a maximum of 4 mL talimogene laherparepvec. Subjects in Cohort 1 will be administered 10⁶ PFU/mL of talimogene laherparepvec in the first cycle. Twenty-one (+3) days later they will be administered 10⁷ PFU/mL of talimogene laherparepvec to start the second cycle. Subsequent cycles (1 dose per cycle) will be given every 21 days (Q21D) (± 3 days), for a total of 6 cycles with an optional 6 additional cycles (see Section 3.1.3).

Cohort 2 will enroll from 3 to 6 DLT-evaluable subjects administering a maximum of 4 mL talimogene laherparepvec. Subjects in Cohort 2 will be administered 10⁶ PFU/mL of talimogene laherparepvec for the first cycle. Twenty-one (21) (+ 3) days later they will be administered 10⁸ PFU/mL of talimogene laherparepvec to start the second cycle. Subsequent cycles (1 dose per cycle) will be given every 21 days (Q21D) (± 3 days), for a total of 6 cycles with an optional 6 additional cycles (see Section 3.1.3).

Cohort 3 will enroll from 3 to 6 DLT-evaluable subjects administering a maximum of 8 mL talimogene laherparepvec. Subjects in Cohort 3 will be administered 10^6 PFU/mL of talimogene laherparepvec for the first cycle, and 10^8 PFU/mL of talimogene laherparepvec, up to 8 mL, 21 days later (+ 3 days) and Q21D (\pm 3 days) for a total of 6 cycles, with an optional 6 additional cycles (see Section 3.1.3).

Cohort 4 will be opened only if any of the following scenarios occur: 1) DLT rate \geq 1/3 in Cohort 2; 2) DLT rate \geq 1/3 in Cohort 3 and Part 2 dose for talimogene laherparepvec not determined yet; or 3) DLT rate \geq 1/3 in Cohort 3 and Part 2 concentration for talimogene laherparepvec is determined to be 10^7 PFU/mL. Subjects in this cohort will be administered a maximum of 8 mL talimogene laherparepvec. Subjects will be administered 10^6 PFU/mL of talimogene laherparepvec for the first cycle, and 10^7 PFU/mL of talimogene laherparepvec, up to 8 mL, 21 days later (+ 3 days) and Q21D (\pm 3 days) for a total of 6 cycles, with an optional 6 additional cycles (see Section 3.1.3).

If both Cohorts 3 or 4 and the combination cohorts (5 or 6) are open in the same institution, subjects with a tumor burden who can receive 8 mL (see Section 6.2.1.1) enrollment into Cohorts 3 or 4 must be strongly preferred until the MTV in monotherapy is determined.

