The DLRT will meet whenever 3 to 6 subjects in each monotherapy dose cohort (Cohorts 1, 2, 3, and 4) of Part 1 or when a sufficient number of additional subjects (per the DLRT Charter), in the combination treatment cohorts (Cohorts 5 and 6 [including 6a and 6b]) in Part 1 are evaluable for subject incidence of DLT, and a decision regarding cohort escalation/modification is being considered. The DLRT will declare a dose safe for Cohorts 1, 2, 3, and 4 if the subject incidence of DLT is < 1/3 during the DLT evaluation period subject to the following rules:

Monotherapy Cohorts (Cohorts 1, 2, 3, and 4) of Part 1. See Section 3.1.4.2 below for combination therapy (Cohorts 5 and 6):

- If no subjects among the initial 3 evaluable subjects in Part 1 experience DLT, then the dose will be deemed safe.
- If 1 subject among the initial 3 evaluable subjects in Part 1 experiences DLT, an additional 3 evaluable subjects will be enrolled.
- If < 2 subjects among the expanded cohort of 6 evaluable subjects in Part 1 experience DLT, then the dose will be deemed safe.
- If ≥ 2 subjects among the initial 3 evaluable subjects or among the expanded cohort of 6 evaluable subjects experiences a DLT, then the dose will be declared not safe.

Additional DLRT meetings will occur after additional DLT-evaluable subjects in each dose cohort of Part 1 of Group A and Group B, respectively, are enrolled per above DLT rules. The MTC will be determined as the highest concentration (either 10^7 or 10^8 PFU/mL) evaluated with a subject incidence of DLT $< 1/3$ between Cohorts 1 and 2, and the MTV will be determined as the highest volume (4 or 8 mL) evaluated with a subject incidence of DLT $< 1/3$ between Cohorts 1, 2, 3, and 4. The MTC for Part 2 is established from Cohorts 5 and 6. If the initial MTV in Part 2 is 4 mL, the MTV for Part 2 will change to 8 mL, if and when, safety of administering the higher volume is established from Cohorts 3 and 4 in Part 1.

3.1.4.2 Safety Evaluation for Combination Therapy in Parts 1 and 2

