- 107 Cohort 3 and 4: sum of tumor diameters from injectable lesions is at least 8 cm (or possibly greater if there are lesions with necrotic cores) and must be eligible to receive > 4 mL of talimogene laherparepvec as defined in Section 6.2.1.1
- 108 Eastern Cooperative Oncology Group (ECOG) performance status of 0 or 1 (see Appendix G)
- 109 Life expectancy approximately 5 months or more
- 110 Adequate organ function determined within 10 days prior to enrollment, defined as follows:
- Hematological (without need for transfusion and or growth factor support within 10 days):
 - ANC $\geq 1500/\text{mm}^3$ ($1.5 \times 10^9/\text{L}$)
 - platelet count $\geq 100\,000/\text{mm}^3$ ($100 \times 10^9/\text{L}$)
 - hemoglobin ≥ 9 g/dL (90 g/L)
 - Renal:
 - serum creatinine $\leq 1.5 \times \text{ULN}$, or 24-hour creatinine clearance ≥ 60 mL/min for subject with creatinine levels $> 1.5 \times \text{ULN}$. (Note: Creatinine clearance need not be determined if the baseline serum creatinine is within normal limits. Creatinine clearance should be calculated per institutional standard).

- Hepatic:
 - serum TBL $\leq 1.5 \times$ ULN
 - AST $\leq 5 \times$ ULN
 - ALT $\leq 5 \times$ ULN
 - Alkaline phosphatase (ALP) $\leq 5 \times$ ULN
- Coagulation:
 - Prothrombin time (PT) or INR $\leq 1.5 \times$ ULN partial thromboplastin time (PTT) or activated PTT (aPTT) $\leq 1.5 \times$ ULN

111 Child-Pugh score of A ([Appendix F](#))

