6.2.1.2 Dosage Adjustments, Delays, Rules for Withholding or Restarting, Permanent Discontinuation

Dose concentration reductions of talimogene laherparepvec are not permitted. However, a reduction in the volume injected due to a disease response is permitted.

For subjects that have an INR of > 1.5 or platelet $< 50,000/\text{mm}^3$ ($50 \times 10^9/\text{L}$) prior to injection, talimogene laherparepvec administration should be delayed until INR is ≤ 1.5 or platelet $\geq 50,000/\text{mm}^3$ ($50 \times 10^9/\text{L}$) without transfusion. Any planned correction of INR or platelet count with transfusion prior to injection should be first discussed and approved with the sponsor medical monitor.

If a subject experiences any of the following treatment-related toxicities, talimogene laherparepvec administration should be delayed until the toxicity has resolved to at least CTCAE version 4.03 grade 1:

- grade 2 or greater immune-mediated adverse events, with the exception of vitiligo.
- grade 2 or greater allergic reactions.
- any other grade 3 or greater hematologic toxicity
- any grade 3 or higher non-hematologic laboratory value unless deemed not clinically important per both investigator and sponsor.

For hepatotoxicity stopping rules refer to Section 6.4.

If a subject requires corticosteroid dosing of > 10 mg prednisone daily (or equivalent, eg, 1.5 mg dexamethasone) for any reason, talimogene laherparepvec and pembrolizumab dosing must be held until the corticosteroid dose has decreased to ≤ 10 mg prednisone daily (or equivalent).

All necessary supportive care shall be available to subjects except for those listed in Section 6.9. Talimogene laherparepvec treatment should be continued based on the potential risk/benefit assessment of the subject.

If talimogene laherparepvec treatment was delayed by > 2 weeks, that dose will be deemed to have been missed and the subject will proceed to the next scheduled treatment visit.

If talimogene laherparepvec dosing is delayed by more than 6 weeks from the date of the planned dose (ie, approximately 9 weeks from the previous dose) due to the occurrence of an adverse event that is considered related to talimogene laherparepvec, the subject must be permanently taken off talimogene laherparepvec treatment.

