10.1.2 Analysis Sets

DLT Analysis Set: The DLT analysis set will include DLT-evaluable subjects enrolled in Part 1 defined as follows:

- **Monotherapy Cohorts:** Subjects who have had the opportunity to be on treatment for at least 6 weeks from the initial dosing of study treatment and have received at least 1 additional dose of talimogene laherparepvec
- **Combination Cohorts:** Subjects who have had the opportunity to be on treatment for at least 6 weeks from the initial dosing of study treatment, and have received at least 2 doses of talimogene laherparepvec and pembrolizumab in combination
- **Subjects experiencing a DLT:** Have a DLT during the DLT-evaluation period after at least 1 dose of talimogene laherparepvec (for monotherapy cohorts) and talimogene laherparepvec and pembrolizumab (for combination cohorts)

Full Analysis Set: For efficacy analyses of talimogene laherparepvec monotherapy, the full analysis set will be defined as all subjects who received at least 1 dose of talimogene laherparepvec and no treatment with systemic pembrolizumab, and for efficacy analyses of talimogene laherparepvec in combination with systemic pembrolizumab, it will be defined as all subjects who received at least 1 dose of talimogene laherparepvec and at least 1 dose of pembrolizumab in combination.

Safety Analysis Set: The safety analysis set will be defined as all subjects who received study therapy. For monotherapy cohort, subjects will be included for analysis of safety if they received at least 1 dose of talimogene laherparepvec. For the combination therapy cohorts or part 2, subjects will be included for analysis of safety if they received at least 1 dose of talimogene laherparepvec or at least 1 dose of pembrolizumab.

Covariates and Subgroups

The following covariates may be used whenever applicable to examine efficacy and safety in subgroups or in multivariate analyses:

- Region, if applicable (USA vs non-USA)
- Age at baseline (< 50, ≥ 50; < 65, ≥ 65; < 75, ≥ 75 years)
- Baseline LDH (≤ ULN vs > ULN)
- Gender (Female vs Male)
- Baseline ECOG (0 vs 1)
- Baseline sum of lengths of measurable lesions
- Baseline sums of lengths of measurable liver lesions
- Prior exposure to chemo therapy (Yes vs No)
- HSV-1 serostatus (Yes vs No)
- Maximum talimogene laherparepvec volume at highest concentration per visit (≤ 4 mL vs > 4 mL)
- Baseline HBV or HCV status
- Baseline Microsatellite Instability status for CRC subjects

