10.3.1.2 Interim Safety Analysis (Part 2)

An interim safety data review will occur for each tumor type separately after approximately 10 subjects have been treated in Part 2 with the specific tumor type with at least 6 weeks of follow-up.

Additional safety analyses may be conducted as warranted during Part 2 if a DLT event occurs in the first 4 DLT-evaluable subjects or after a target of approximately 6 and 16 DLT-evaluable subjects. As appropriate the DLRT will be convened to monitor safety.

A total volume > 4 mL of talimogene laherparepvec may be allowed in Part 2 with systemic pembrolizumab if it is declared safe without pembrolizumab in Part 1. In this event, the DLRT will also monitor safety in Part 2 separately among subjects in non-HCC (Group A) and HCC (Group B) arms that receive at least 1 dose of talimogene laherparepvec with a total volume > 4 mL at the combination MTC with systemic pembrolizumab. Subjects will be included in the safety assessment of > 4 mL with at least 3 weeks follow-up from an initial total volume > 4 mL at the combination MTC.

Safety analyses, including analyses of the subjects receiving a total volume > 4 mL talimogene laherparepvec, will be performed at the time of the planned analyses for each tumor type arm or more frequently at the DLRTs discretion.

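### The 8 mL maximum tolerated volume is read off a nominal cohort cap: neither DLT evaluability nor the MTV rule considers delivered volume, and a compliant Cohort 3 or 4 subject can receive as little as 5 mL

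*Protocol*

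**What the plan says.** Protocol Section 3.1.1.1 sets the cohort volume as a cap: "Cohort 3 will enroll from 3 to 6 DLT-evaluable subjects administering a maximum of 8 mL talimogene laherparepvec". Cohort 4 is worded in the same way. Section 3.1.4.1 then says that "the MTV will be determined as the highest volume (4 or 8 mL) evaluated with a subject incidence of DLT" below 1/3. The 3+3 rule in that section has two routes to a safe declaration:

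- "If no subjects among the initial 3 evaluable subjects in Part 1 experience DLT, then the dose will be deemed safe"
- "If < 2 subjects among the expanded cohort of 6 evaluable subjects in Part 1 experience DLT, then the dose will be deemed safe"

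DLT evaluability in the monotherapy cohorts (Protocol 10.1.2, repeated in SAP 6.3) asks that subjects have had the opportunity for six weeks on treatment and "have received at least 1 additional dose of talimogene laherparepvec". Section 3.1.4.1 adds only that early discontinuation or loss to follow-up for a reason other than DLT makes a subject non-evaluable. No volume condition appears in any of the three places.

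For Cohorts 3 and 4, inclusion criterion 107 requires that the "sum of tumor diameters from injectable lesions is at least 8 cm" and that the subject be eligible for more than 4 mL under Section 6.2.1.1. The volume per lesion follows Table 3, which scales it by diameter. Injection stops at the daily cap or when injectable lesions run out. Section 6.2.1.2 adds that "a reduction in the volume injected due to a disease response is permitted".

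**The concern.** The MTV is a Part 1 primary objective. Combination Cohorts 5 and 6 are capped at 4 mL, so monotherapy Cohorts 3 and 4 are the only Part 1 evidence on larger volumes. Under Table 1, a safe Cohort 3 in either group opens up to 8 mL in Part 2 for both groups, and Section 3.1.2 describes 8 mL as established.

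The observed DLT rate belongs to the volumes that were given. If those are mostly below 8 mL, attaching the rate to 8 mL claims more than the data show. The SAP does not correct for this. Section 9.6.1 summarises DLT as a binary variable, and Section 9.6.6 tabulates exposure separately, with no link between a subject's volume and that subject's DLT status.

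**Working it through.** **The plan's own figure.** Under the 3+3 rule a cohort is declared safe after 0 DLTs in 3 subjects, or after 1 in 3 followed by 0 in 3 more:

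P(safe) = (1 − p)³ + 3p(1 − p)² × (1 − p)³

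For p = 0.1, 0.2, 0.3, 0.4 and 0.5 this gives 0.906, 0.709, 0.494, 0.309 and 0.172. Protocol Table 16 states 0.91, 0.71, 0.49, 0.31 and 0.17. All five agree.

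**Lowest volume under compliant dosing.** The inputs are criterion 107 (sum of diameters at least 8 cm and capacity above 4 mL) and the Table 3 bands for Cohorts 3 and 4. For lesions less than 75% necrotic the bands are: under 2 cm, 1 mL; 2 to under 4 cm, 2 mL; 4 to under 6 cm, 4 mL; 6 to under 8 cm, 6 mL; 8 cm or more, 8 mL.

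- Below 8 cm, every band carries less than 2 cm of diameter per mL. A total of 4 mL therefore covers less than 4 × 2 = 8 cm, and a subject with 8 cm must draw more than 4 mL. The table works in whole mL, so the floor is 5 mL.
- The floor is attained. Lesions of 3.5 + 3.5 + 1.0 = 8.0 cm give 2 + 2 + 1 = 5 mL. Five lesions of 1.6 cm (8.0 cm) give 5 × 1 = 5 mL.
- For lesions at least 75% necrotic, 8 cm can draw only 4 mL (for example 4.9 + 3.1 cm, 2 mL each). The more-than-4-mL clause excludes that subject, so the floor stays at 5 mL.
- 5/8 = 62.5% of the nominal volume.

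A volume below 5 mL needs lesion shrinkage before the second dose, or under-delivery. Neither makes the subject non-evaluable.

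**Effect on the safe declaration.** The documents give no DLT rates by volume, so the pairs below are assumptions, shown as a range. The middle column lets half the subjects on average receive full volume, so p is the mean of the two rates (0.2, 0.3 and 0.4 in turn).

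| True DLT rate, full volume / delivered volume | P(safe), all at full volume | P(safe), half at full volume | P(safe), none at full volume |
|---|---|---|---|
| 0.3 / 0.1 | 0.49 | 0.71 | 0.91 |
| 0.4 / 0.2 | 0.31 | 0.49 | 0.71 |
| 0.5 / 0.3 | 0.17 | 0.31 | 0.49 |

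**The case against.** The plan has real safeguards. Criterion 107 is an entry gate above 4 mL. Section 6.2.1.1 tells sites to inject all reasonably injectable lesions to the maximum available. Section 3.1.1.1 strongly prefers subjects who can receive 8 mL for Cohorts 3 and 4 when combination cohorts are open at the same site. Protocol 10.1.2 and SAP 4.1 list maximum volume (≤ 4 vs > 4 mL) as a possible subgroup. These stand, and they rule out a reading a reader might infer: that eligible, fully dosed subjects could support 8 mL on 4 mL or less. They do not close the gap. The gate concerns capacity at entry and its cut is 4 mL, not 8. The preference is not an evaluability rule. The subgroup is optional and does not feed the MTV.

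It can also be argued that what was tested is a capped, size-scaled regimen, and that Table 3 footnote a carries one of its two guidelines into Part 2. For liver lesions that is fair, and it is why the MTV should be worded as a cap. It does not extend to Table 4, a different guideline for cutaneous, subcutaneous and nodal lesions, whose bands above 4 mL depend on an 8 mL MTV.

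A reader might also take Section 10.3.1.2 as proof of inconsistency, since its Part 2 assessment of more than 4 mL counts subjects "with at least 3 weeks follow-up from an initial total volume" above 4 mL. That goes too far. Criterion 107 applies only to Cohorts 3 and 4, so Part 2 has to identify such subjects afterwards.

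Finally, the DLRT may weigh all clinical data, and its Charter is not among the documents. The protocol and SAP refer to it for numbers of subjects, mTPI details and Part 2 guidelines, and they define evaluability without a volume condition.

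**Conclusion.** The point holds for Cohorts 3 and 4, where volume is under test. The 8 mL MTV can rest on subjects none of whom received 8 mL, with 5 mL as the floor for a compliant subject dosed to the Table 3 maximum. The floor follows from the documents. The effect on the safe declaration rests on assumed DLT rates and ranges from 0.49 vs 0.91 to 0.17 vs 0.49 when no subject receives full volume.

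Two stronger conclusions are tempting. One is that the MTV was wrongly set or that 8 mL is unsafe. The documents report no delivered volumes and no DLTs by volume, so they cannot show this. The other is that Table 16 is in error. It is not: it is correct for the DLT rate at the volumes given, which need not be the rate at 8 mL. Enrollment and intrahepatic injection have stopped, so the point now bears on what the study report may claim for a primary objective.

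**What to change.** Leave the primary DLT set and the 3+3 decision unchanged. Redefining them after enrollment in an open-label study would be retrospective.

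- In SAP 9.6.1 and 9.6.6, tabulate for each DLT-evaluable subject in Cohorts 3 and 4 the total volume delivered at the 10^6 PFU/mL dose and at the first 10^7 or 10^8 PFU/mL dose, beside DLT status.
- Add a supplementary DLT incidence by delivered volume, using the documents' own ≤ 4 vs > 4 mL cut and showing how many received the full 8 mL. Count every DLT whatever the volume, including one before the second dose.
- In the clinical study report, describe the MTV as up to 8 mL, dosed by Table 3, and give the range of volumes received. State plainly if few or no evaluable subjects received 8 mL, or more than 4 mL, at the test concentration.

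No volume threshold or dose rule is proposed. The cost is one extra table, from volumes that Section 6.2.1.1 already has recorded on the CRF, and a more qualified 8 mL claim.

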3.1.2 Study Design for Part 2 (Non-HCC and HCC Groups)

Part 2 is a 2-stage design to evaluate the efficacy of talimogene laherparepvec in combination with systemic pembrolizumab separately by tumor type. The DLRT will consider prospective guidelines in the DLRT Charter to monitor safety in Part 2

separately by tumor type and, if introduced, talimogene laherparepvec total volumes > 4 mL within Group A and Group B as discussed in Section 10. Subjects will be enrolled into one of the following treatment groups and arms based on the underlying tumor type:

- Group A (non-HCC):
 - Arm I: Hormone receptor positive breast cancer
 - Arm II: TNBC
 - Arm III: CSCC
 - Arm IV: BCC
 - Arm V: CRC
- Group B (HCC):
 - Arm VI: HCC with or without viral hepatitis

Part 2 (Group A) of the study will enroll subjects of non-HCC tumors (hormone receptor positive BC, TNBC, CSCC, CRC, BCC). Subjects will be enrolled separately into each tumor type. Stage 1 of Part 2 (Group A) will begin enrolling after MTC has been determined from Cohort 5 and 6 in Part 1.

Part 2 (Group B) of the study will enroll subjects with HCC with and without viral hepatitis. Stage 1 of Part 2 (Group B) will begin enrolling after MTC has been determined from Cohorts 5 and 6 in Part 1.

Subject enrollment and study conduct during Part 2 of the study will progress independently in the non-HCC and HCC groups.

During Stage 1 of Part 2, non-HCC and HCC groups will enroll approximately 10 subjects for each tumor type arm (5 tumor type arms in Group A and 1 tumor type arms in Group B with and without viral hepatitis). Subjects with specific tumor types from the combination cohorts in Part 1 (Cohorts 5 and 6) that are treated at the MTC used in Part 2, will not be included as part of the enrollment numbers for that tumor type arm in Part 2. Subjects enrolled in Part 2 will initially be administered up to 8 mL of talimogene laherparepvec MTC determined from Cohorts 5 or 6 in Part 1.

Administration of up to 8 mL of talimogene laherparepvec was established from Part 1, Cohort 3 of either Group, any newly enrolled subjects in Part 2 can be administered up to 8 mL of talimogene laherparepvec. No intrasubject concentration or volume

escalation is allowed. The primary analysis of efficacy will include subjects that receive any volume of talimogene laherparepvec (monotherapy cohorts) and subjects that receive any volume of talimogene laherparepvec and pembrolizumab (combination cohorts). Stage 1 of a 2-stage efficacy assessment will occur once 10 subjects have been enrolled in a tumor type arm. Stage 1 efficacy assessments will occur separately per tumor type arm. If efficacy is not futile, Stage 2 will open for that particular tumor type arm where approximately an additional 11 subjects can be enrolled.

3.1.3 Optional Additional Dosing for Talimogene Laherparepvec

After the subjects in either Part 1 or Part 2 have received the first 6 cycles of talimogene laherparepvec, there is an option to continue dosing with up to 6 additional cycles (Part 1 only) or a maximum of 35 cycles (Part 2) of talimogene laherparepvec at the same dose level as in cycles 2 to 6 provided that the subject has lesions to inject, has not reached a confirmed progressive disease (PD) by modified immune-related response criteria (irRC) simulating RECIST version 1.1 (irRC-RECIST; Nishino et al, 2014), has not had rapid clinical deterioration or worsening symptomatic disease, has not had intolerance of treatment, has no significantly better alternative treatment options in the opinion of the investigator, and agrees to the additional doses of talimogene laherparepvec after investigator discussion with the medical monitor (medical monitor approval required in Part 1 only). In Part 2, additional dosing of talimogene laherparepvec beyond a total of 12 cycles of talimogene laherparepvec may be allowed if in the opinion of the investigator and after discussion with the medical monitor, the subject is deriving clinical benefit from the study regimen, the subject is still receiving pembrolizumab.

3.1.4 Safety Evaluation for Parts 1 and 2

A DLRT, consisting of an Amgen medical clinician, safety representative, biostatistician, Global Clinical Study Manager (GCTM), representative(s) from Merck, and at least one participating investigator who enrolled subjects into Part 1 and/or Part 2, will review the safety data to evaluate the subject incidence of DLTs and adverse events.

Representative(s) from Merck will participate in DLRT meetings for all cohorts (voting member only for cohort 5 and 6 of Part 1 and all cohorts in Part 2). The DLRT will make recommendations in Part 1 according to the DLT 3 + 3 rules for monotherapy cohorts, mTPI up-and-down design rules for combination cohorts, and in Part 2 the DLRT will make recommendations considering prospective guidelines to monitor safety, in the DLRT Charter. For each dosing cohort in Part 1, the DLRT will recommend either to enroll more subjects for DLT evaluation, to prematurely stop enrollment, or to declare the

dose tolerable. In Part 2, the DLRT may consider reducing the RP2D talimogene laherparepvec concentration and/or discontinuation of total volumes > 4 mL, if introduced. If the concentration is reduced in Part 2 for a tumor type arm, then the sample size considerations for the 2-stage futility and efficacy analyses of that tumor type arm will include only subjects treated at the reduced concentration. The DLRT can consider the totality of available clinical data when reviewing a given cohort.

3.1.4.1 Rules for DLT Evaluation and Dose Escalation for Part 1

Monotherapy Cohorts:

The DLT evaluation period for a given subject will consist of the period between the initial 10^6 PFU/mL dose of talimogene laherparepvec and 3 weeks following the initial 10^7 or 10^8 PFU/mL dose of talimogene laherparepvec. A subject will be considered to have had a DLT if they experience a DLT event (as outlined in Section 3.1.4.3) during the DLT evaluation period. Any subject who discontinues treatment or is lost to follow-up before the end of the DLT evaluation period for any reason other than DLT will not be considered evaluable for DLT and may need to be replaced by another subject in the same cohort.

Combination Cohorts:

The DLT evaluation period for a given subject will consist of the period between the initial 10^6 PFU/mL concentration of talimogene laherparepvec and 3 weeks following the initial 10^7 or 10^8 PFU/mL dose of talimogene laherparepvec. Any subject who has not received at least 2 doses of talimogene laherparepvec (10^6 , and 10^7 or 10^8 PFU/mL) and 2 doses of pembrolizumab, will not be considered DLT-evaluable unless they experience a DLT after the first dose. A subject will be considered to have had a DLT if they experience a DLT event (as outlined in Section 3.1.4.3) during the DLT evaluation period. Any subject who discontinues treatment, or is lost to follow-up before the end of the DLT evaluation period for any reason other than DLT, will not be considered evaluable for DLT and may need to be replaced by another subject in the same cohort.

The DLRT will meet whenever 3 to 6 subjects in each monotherapy dose cohort (Cohorts 1, 2, 3, and 4) of Part 1 or when a sufficient number of additional subjects (per the DLRT Charter), in the combination treatment cohorts (Cohorts 5 and 6 [including 6a and 6b]) in Part 1 are evaluable for subject incidence of DLT, and a decision regarding cohort escalation/modification is being considered. The DLRT will declare a dose safe for Cohorts 1, 2, 3, and 4 if the subject incidence of DLT is < 1/3 during the DLT evaluation period subject to the following rules:

Monotherapy Cohorts (Cohorts 1, 2, 3, and 4) of Part 1. See Section 3.1.4.2 below for combination therapy (Cohorts 5 and 6):

- If no subjects among the initial 3 evaluable subjects in Part 1 experience DLT, then the dose will be deemed safe.
- If 1 subject among the initial 3 evaluable subjects in Part 1 experiences DLT, an additional 3 evaluable subjects will be enrolled.
- If < 2 subjects among the expanded cohort of 6 evaluable subjects in Part 1 experience DLT, then the dose will be deemed safe.
- If ≥ 2 subjects among the initial 3 evaluable subjects or among the expanded cohort of 6 evaluable subjects experiences a DLT, then the dose will be declared not safe.

Additional DLRT meetings will occur after additional DLT-evaluable subjects in each dose cohort of Part 1 of Group A and Group B, respectively, are enrolled per above DLT rules. The MTC will be determined as the highest concentration (either 10^7 or 10^8 PFU/mL) evaluated with a subject incidence of DLT $< 1/3$ between Cohorts 1 and 2, and the MTV will be determined as the highest volume (4 or 8 mL) evaluated with a subject incidence of DLT $< 1/3$ between Cohorts 1, 2, 3, and 4. The MTC for Part 2 is established from Cohorts 5 and 6. If the initial MTV in Part 2 is 4 mL, the MTV for Part 2 will change to 8 mL, if and when, safety of administering the higher volume is established from Cohorts 3 and 4 in Part 1.

3.1.4.2 Safety Evaluation for Combination Therapy in Parts 1 and 2

For subjects enrolled in combination therapy (Cohort 5 and 6) in Part 1, safety will be evaluated separately for each Group (A and B) with a common mTPI up-and-down design to determine the talimogene laherparepvec MTC for each Group with a target DLT rate of 40%. For Cohorts 5 and 6 in Part 1, the mTPI model will be used for each Group (A and B). A review of safety data in Part 1 will occur when a sufficient number of additional DLT-evaluable subjects (per the DLRT Charter), have been enrolled in a Group.

For Part 2, the DLRT will consider prospective guidelines in the DLRT Charter to monitor safety within Group A and Group B and, if introduced, talimogene laherparepvec total volumes > 4 mL within Group A and Group B. During Part 2 of the study, a planned review of efficacy data will occur after a total of 10 treated subjects have been enrolled in a particular tumor type arm with at least 20 weeks minimum potential follow-up (see Section 10.2 and Section 10.3.1.2 for more details). An interim safety data review will occur for each tumor type separately after approximately 10 subjects have been treated in Part 2 with the specific tumor type with at least 6 weeks of follow-up.

The enrollment will be suspended after 10 treated subjects for a particular tumor type for the Stage 1 efficacy futility analysis if a non-futile efficacy outcome cannot be verified after the 10th treated subject. The subject incidence of DLT and adverse events will be monitored in Part 2 and additional safety analyses may be conducted as warranted during the conduct of the study at the discretion of the DLRT.

